8.4.4. Vital Signs

Vital signs will include oral temperature (°C), respiratory rate (breaths per minute), heart rate (beats per minute [bpm]), and blood pressures (mmHg). Heart rate and blood pressure were collected in supine position and standing position at all scheduled time points.

Vital sign results and mean changes from baseline will be summarized by scheduled visit. This will also include the summary of last values on treatment and on study assessments. Potentially clinically significant values as outlined in [Table 14](#) will be summarized by treatment and for anytime on treatment, last value on treatment, after the last dose of treatment (follow-up period). By-participant listing of vital signs will also be provided.

Table 14. Potentially Clinically Significant Values for Vital Sign Parameters

Vital Sign	Units	Criteria for PCS Values (Observed values)		Criteria for PCS values (Change from Baseline values)	
		High	Low	Increase	Decrease
Heart rate (supine and standing)	Beats/min	>120	<40	NA	NA
Respiratory Rate	Breaths/min	>20	<8	NA	NA
Systolic blood pressure (supine and standing)	mmHg	>180	<90	≥30	≥30
Diastolic blood pressure (supine and standing)	mmHg	>110	<50	≥20	≥20
Supine – Standing Systolic Blood Pressure	mmHg	≥20			

Vital Sign	Units	Criteria for PCS Values (Observed values)		Criteria for PCS values (Change from Baseline values)	
		High	Low	Increase	Decrease
Supine – Standing Diastolic Blood Pressure	mmHg	≥10			
Orthostatic hypotension: supine – standing SBP and DBP	mmHg	SBP ≥20 and DBP ≥10			
Possible orthostatic hypotension: supine – standing SBP and DBP	mmHg	SBP ≥20 or DBP ≥10			

8.4.5. Physical Examination

A full physical examination is to be conducted during Screening and at Day 42 (± 2 days). At other visits, physical examinations will include a brief assessment of general appearance, cardiovascular, respiratory, gastrointestinal, and neurological systems and followed by a targeted physical assessment as needed. A by-participant listing of physical examination findings will also be provided.

8.4.6. Columbia Suicide Severity Rating Scale

Suicidality data collected on the C-SSRS is collected during the clinical visits at Screening, Days 1, 14, 28, and 42. The C-SSRS includes ‘yes’ or ‘no’ responses for assessment of suicidal ideation and behavior as well as numeric ratings for severity of ideation, if present (from 1 to 5, with 5 being the most severe).

The participant’s non-suicidal self-injurious behaviors is also assessed separately as part of C-SSRS.

The “Baseline/Screening” C-SSRS form will be completed at screening (lifetime history and in the past 1 month or past 1 year). The “Since Last Visit” C-SSRS form will be completed at all subsequent time points.

The assessments for suicidal ideation are ranked as follows with 5 being the worst:

1. Wish to be dead
2. Non-specific active suicidal thoughts
3. Active suicidal ideation with any methods
4. Active suicidal ideation with some intent
5. Active suicidal ideation with specific plan

The assessments for suicidal behavior are ranked as follows with 5 being the worst:

1. Preparatory acts or behavior
2. Aborted attempt
3. Interrupted attempt
4. Actual attempt (non-fatal)
5. Completed suicide

Suicidal behavior is considered worse than suicidal ideation.

Baseline for each question is defined as the worst of the assessments done before the first dose of IP, excluding the lifetime version. This will typically include the ‘past 1-month/past 1-year’ version from screening and ‘since last visit version’ from Day 1, as well as any unscheduled visits done before the first dose of IP; any Yes will make the baseline value as Yes.

The number and percentage of participants with at least one response of ‘Yes’ to any C-SSRS suicidal ideation or suicidal behavior item, as well as for Participant’s non-suicidal self-injurious behavior, will be summarized first by visit, then separately for baseline and anytime post-baseline.

Summary of shift from baseline in C-SSRS suicidal ideation and suicidal behavior will be presented for the following categories (no suicidal ideation/behavior, suicidal ideation, and suicidal behavior) for each scheduled assessment time point. If there is no ‘Yes’ response to all assessments in suicidal ideation and behavior, then the category for the table is considered as ‘No suicidal ideation/behavior’. If any of the assessments in suicidal behavior is Yes, the category is considered as ‘Suicidal behavior’. If any of the assessments in suicidal ideation is Yes but all assessments in suicidal behavior is No, the category is considered as ‘Suicidal ideation’. If the participant has both suicidal ideation as well as suicidal behavior, the participant will be counted under suicidal behavior only.

In addition, a summary of shift in suicidal ideation from baseline maximum rank score for anytime post-baseline maximum rank score will be presented. Maximum score 0 refers to all ‘No’ for all assessments in the desired period for all 5 questions on suicidal ideation. A graph of distribution of participants with suicide-related events based on the C-SSRS scores over time by treatment group will be generated. A listing of suicidal ideation and suicidal behavior will be provided.

8.4.7. Other Safety Analysis

Not applicable.

[REDACTED]

[REDACTED]

[REDACTED]

9. SUMMARY OF INTERIM AND DMC ANALYSES

Not applicable.

11. LIST OF APPENDICES

APPENDIX A. SCHEDULE OF ASSESSMENTS – HUNTINGTON’S DISEASE

Assessments	Screening Period		Treatment Period			Follow-up Day 42 (±2 days) or ET
	Days -28 to -2	Day-1	Day 1	Day 14 (±2 days)	Day 28 (±2 days)	
Informed consent ^a	X					
Inclusion/exclusion criteria	X	X	X			
Randomization ^b			X			
Family/medical history and demographics ^c	X					
Participant training ^d	X	X	X			
Body weight	X				X	X
Body height	X					
Vital signs (including orthostatics) ^e	X	X		X	X	X
Physical examination ^f	X	X			X	X
CAG test (if not collected as part of medical history) ^g	X					
FSH test ^h	X					
Serology test ⁱ	X					
12-lead ECG ^j	X	X			X	X
Clinical laboratory assessments ^k	X	X			X	X
Urine drug test ^l	X	X	X	X	X	X
Alcohol test ^l	X	X	X	X	X	X
Cigarette/tobacco use assessment ^m	X		X	X	X	X
Pregnancy test ⁿ	X		X		X	X
C-SSRS (Screening)	X					
C-SSRS (since last visit)			X	X	X	X

Assessments	Screening Period		Treatment Period			Follow-up
	Days -28 to -2	Day-1	Day 1	Day 14 (±2 days)	Day 28 (±2 days)	Day 42 (±2 days) or ET
Cognitive test (HD-CAB) ^t	X		X	X	X	X
Daily Mobile Assessments ^x		X-----X				
IP self-administration ^y			X (once daily in the morning)			
IP dispensation ^z		X	X			
IP accountability/return ^{aa}				X	X	
AEs/SAEs			X (from time of ICF throughout the duration of participation)			
Prior and concomitant medications	X-----X					

Abbreviations: AE = adverse event; CAP = CAG-Age-Product; [REDACTED]

[REDACTED] COVID-19 = coronavirus disease 2019;

C-SSRS = Columbia–Suicide Severity Rating Scale; [REDACTED]

[REDACTED] ECG = electrocardiogram; ET = early termination; FSH = follicle-stimulating hormone; HD = Huntington's Disease; HD-CAB = Huntington's Disease Cognitive Assessment Battery; [REDACTED]

[REDACTED] HIV = human immunodeficiency virus; ICF = informed consent form; IP = investigational product; [REDACTED] O = optional; [REDACTED]

SAE = serious adverse event; [REDACTED]

a. Both participants and study partners (if applicable) will be consented during the Screening Period.

Note: On screening (Days -28 to -2), Day 28, and Day 42, safety assessments [REDACTED] [REDACTED] may be done on separate day(s) than the cognitive assessments, if need be, provided that all assessments are completed within the specified visit window (± 2 days).

APPENDIX B. SCHEDULE OF ASSESSMENTS – HEALTHY PARTICIPANTS

Assessments	Screening Period		Reliability Assessment Period			Follow-up
	Days - 28 to -2	Day -1	Day 1	Day 14 (±2 days)	Day 28 (±2 days)	
Informed consent ^a	X					
Inclusion/exclusion criteria	X	X	X			
Medical history and demographics ^b	X					
Participant training ^c	X	X	X			
Body weight	X					X
Body height	X					
Vital signs (including orthostatics) ^d	X	X				X
Physical examination ^e	X	X				X
FSH test ^f	X					
Serology test ^g	X					
12-lead ECG ^h	X	X				X
Clinical laboratory assessments ⁱ	X	X				X
Urine drug test	X	X	X	X	X	X
Alcohol test	X	X	X	X	X	X
Cigarette/tobacco use assessment ^j	X		X	X	X	X
Pregnancy test ^k	X		X			X
C-SSRS (Screening)	X					
Daily Mobile Assessments ^p			X-----			X
AEs/SAEs				X		
			(from time of ICF throughout the duration of participation)			

Assessments	Screening Period		Reliability Assessment Period			Follow-up
	Days -28 to -2	Day -1	Day 1	Day 14 (±2 days)	Day 28 (±2 days)	Day 42 (±2 days) or ET
Prior and concomitant medications	X-----					

Abbreviations: AE = adverse event; [REDACTED]

COVID-19 = coronavirus disease 2019; C-SSRS = Columbia–Suicide Severity Rating Scale;

ECG = electrocardiogram; ET = early termination; FSH = follicle-stimulating hormone; HD = Huntington's Disease; HD-CAB = Huntington's Disease Cognitive Assessment Battery, HIV = human immunodeficiency virus; ICF = informed consent form; [REDACTED] SAE = serious

adverse event; [REDACTED]

- a. Participants will be consented during the Screening Period.
- b. In addition to full medical history, all medications and supplements taken within 8 weeks prior to Screening. Information regarding diagnosis and/or hospitalization due to COVID-19 will be documented as part of medical history. The following demographics will be collected: age, race, sex, ethnicity, years of education, employment history, and current employment status.
- c. Participants will be trained by study staff on the use of software applications and devices necessary for the conduct of the study.
- d. Vital signs will include temperature, respiratory rate, heart rate, and blood pressure. Heart rate and blood pressure to be collected in supine position and standing position at all scheduled time points.
- e. A full physical examination is to be conducted during Screening (Days -28 to -2) and at Day 42 (±2 days)/ET. A symptom-directed examination may be conducted at any time at the discretion of the investigator.
- f. Serum FSH test will be conducted at Screening for the female participants who are not surgically sterile to confirm whether a female participant with ≥12 months of spontaneous amenorrhea meets the protocol-defined criteria for being postmenopausal.
- g. To include hepatitis B and C screening tests, HIV-1 and -2 antibody.
- h. A single ECG will be measured after the participant has been in the supine position for at least 5 minutes.
- i. Clinical laboratory assessments will include blood samples for hematology, clinical chemistry, biochemistry, coagulation, and urinalysis. Sample collection may occur at any time.
- j. Data on cigarette use will be collected using the question: "How many packs of cigarettes did you smoke over the past 7 days?" at the time points specified.
- k. Serum pregnancy tests will be conducted for all female participants at Screening; urine pregnancy tests will be conducted at other scheduled time points for female participants that are not postmenopausal or surgically sterile.
- l. [REDACTED]
- m. Cognitive tests at all time points will be performed at the same time of day (±2 hours). The cognitive tests include the Huntington's Disease Cognitive Assessment Battery (HD-CAB; Symbol Digit Modalities Test, One Touch Stockings of Cambridge, Trail Making A and Trail Making B, Hopkins Verbal Learning Test_Revised, Paced Tapping Test, and Emotion Recognition Test) [REDACTED]
[REDACTED]
[REDACTED]
[REDACTED]
[REDACTED]
[REDACTED]
[REDACTED]

p. Daily reminders will be sent to participants via a mobile device to complete assessments on remote device.
Daily assessments include [REDACTED]

[REDACTED] the National Sleep Foundation Sleep Diary. It is recommended that assessments are completed at approximately the same time each day. Daily mobile assessments should be completed in a quiet area of participant's home. If in conflict with clinic visit schedule, remote assessment may be completed in the clinic under observation by the study staff.

Note: On Days 28 and 42, safety assessments [REDACTED] may be done on separate day(s) than the cognitive assessments, if need be, provided that all assessments are completed within the specified visit window (± 2 days).

APPENDIX C. DETAILS OF STATISTICAL METHODOLOGY

Sample SAS Code for T-test

```
proc ttest data=data sides=2 alpha=0.05 h0=0 test=diff;
  class subjgrp;
  var aval;
  ods output statistics=statistics ttests=ttests equality=equality;
run; *Note: if probf > 0.05 reading results from pooled method, if probf > 0.05 reading
results from satterthwaite method;
```

APPENDIX D. HANDLING OF MISSING DATES

Dates missing the day or both the day and month of the year will adhere to the following conventions in order to classify TEAEs and to classify prior and concomitant medications.

In general, listings will present the actual partial or missing values rather than the imputed values that may be used in derivation. In instances where imputed values will be presented, imputed values will be flagged.

Adverse Events

If the AE start date is completely missing, do not impute a date but consider it as TEAE, unless the AE end date is before the initiation of treatment, in which case the AE will be considered prior.

For partial AE start dates:

- When the year is known, but the month and day is unknown, then:
 - If the year matches the year of first dose date and the end date (if present) is after first dose date, or AE is ongoing, then impute as the month and day of the first dose date + 1 day.
 - If the year of AE onset < year of initiation of the treatment, then the month and day will be set to December 31st.
 - If the year of AE onset > the year of initiation of treatment, then the month and day will be set to January 1st.
- If the year and month are known, but the day is unknown, then:
 - If the year of AE onset = the year of initiation of the treatment and:
 - the month of AE onset = the month of initiation of the treatment, then the day will be set to the day of initiation of the treatment.
 - the month of AE onset < the month of initiation of the treatment, then the day will be set to the last day of month.
 - if the month of AE onset > the month of initiation of the treatment, then the day will be set to the 1st day of month.
 - If the year of AE onset < the year of initiation of the treatment, then the day will be set to the last day of month.
 - If the year of AE onset > the year of initiation of the treatment, then the day will be set to the 1st day of month.

If the imputed AE onset date is after the AE stop date, then the onset date will be set to the stop date.

- When the year and day are present and the month is missing, treat it as if the day is missing, and only year is present. Follow the imputation rules for “year is known, but the month and day is unknown”.
- When the year is missing, but the month and/or day is known, treat this date as missing; do not impute.

Prior and Concomitant Medications

If the medication start date is completely missing, do not impute a date but consider it as concomitant, unless the medication end date is before the initiation of IP for HD or day 1 for HP, in which case the medication will be considered prior.

[figure not shown]
For the partial start date of medication:

[figure not shown]
- If the year is present and the month and day are missing, then the month and day will be set to January 1 unless the year is the same as the first dose date then impute the first dose date.
- If the year and day are present and the month is missing, then treat it as if the day is missing and only year is present. Follow the imputation rules for “year is known, but the month and day is unknown”.
- If the year and month are present and the day is missing, then the day will be set to the 1st day of month unless the month is the same as the date of the first dose then impute as the date of the first dose.
- If the imputed start date of medication is after the non-imputed end date of medication, then the start date will be set to the end date of medication.

[figure not shown]
If the medication end date is completely missing, do not impute a date but consider it as concomitant.

[figure not shown]
For the partial end date of medication:

[figure not shown]
- If the year is present and the month and day are missing, then the month and day /will be set to December 31.
- If the year and month are present and the day is missing, then the day will be set to the last day of the month.
- If the year and day are present and the month is missing, then treat it as if the day is also missing. Impute the month and day to be December 31.

[figure not shown]

[figure not shown]

[figure not shown]

[figure not shown]

[figure not shown]

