9.2. Prior Medications, Concomitant Medications, Restrictions, and Contraception Requirements

9.2.1. Prior and Concomitant Medications and/or Supplements

All medications and supplements taken within 8 weeks prior to Screening, all medications used to treat HD regardless of timing, and all nonpharmacological methods (eg, psychosocial, psychotherapeutic) used to treat or prevent neuropsychiatric, functional, and cognitive manifestations of HD will be recorded. Information regarding diagnosis and/or hospitalization due to coronavirus disease 2019 (COVID-19) will be documented as part of medical history, AE collection, and prior/concomitant medication/procedure collection at Screening and throughout the study.

At visits subsequent to Screening, all changes to any medication should be captured. All medications and/or supplements taken from the first dose of IP through the final study visit (including start and end dates, route, dose/units, frequency, and indication) will be recorded on the source document. Any concomitant medication determined necessary for the welfare of the participant with HD may be given at the discretion of the investigator at any time during the study.

Because this study aims to measure effects on cognitive performance, it is important to evaluate single or combined concomitant medications and their doses for their potential effects on cognition. Investigators will carefully review concomitant medications for possible cognitive effects at Screening to determine participant eligibility and throughout the study.

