8.2.5. Prior and Concomitant Medications

This analysis will be based on the Safety Set 1 and Safety Set 2.

Medications will be recorded at each study visit during the study and will be coded using World Health Organization-Drug dictionary (WHODrug-Global-B3) September 2022 B3.

All medications taken within 60 days prior to informed consent through the duration of the study will be recorded. Those medications started and stopped prior to the initiation of the start of IP for HD and day 1 for HP will be denoted “Prior”. Those medications taken prior to the initiation of the IP and continuing beyond the initiation of the IP, or those medications started at the same time or after the initiation of the IP will be denoted “Concomitant” for HD.

Those medications taken prior to day 1 and continuing beyond day 1, or those medications started at the same time or after day 1 will be denoted “Concomitant” for HP.

Medications will be presented according to whether they are “Prior” or “Concomitant” as defined above. If medication dates are incomplete and it is not clear whether the medication are concomitant, it will be assumed to be concomitant.

Missing or partial dates will be imputed for medication. Algorithm for missing or partial start /end date is documented in [Appendix D](#).

Concomitant medications are further categorized as on-treatment and post-treatment as follows:

On-treatment concomitant medications are those that have been used between first and last dose of IP (both inclusive) as well as medications started prior to first dose of IP and continue beyond the initiation of IP.

Post-treatment concomitant medications are those that have been started after the last dose of IP.

Concomitant medications will be summarized on Safety Set using Anatomical Therapeutic Chemical (ATC) level 1 and preferred term by actual treatment group.

By-participant listings of prior and concomitant medications, and concomitant procedures will also be provided.

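### SAP Appendix D resets a late imputed medication start only against a complete end date, so some HD medicines stopped before dosing are classed as concomitant

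*SAP*

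**What the plan says.** SAP Appendix D states that its date conventions serve to separate prior from concomitant medications. Its medication rules that matter here are:

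- **Start, year only:** the month and day are "set to January 1 unless the year is the same as the first dose date then impute the first dose date". No condition refers to the end date.
- **Start, month missing but day present:** "If the year and day are present and the month is missing, then treat it as if the day is missing and only year is" (last word omitted here). The year-only rule then applies.
- **Start, day missing:** first of the month, "unless the month is the same as the date of the first dose then impute as the date of the first dose".
- **End, day missing:** last day of the recorded month. **End, year only or month missing:** 31 December.
- **Reset:** "If the imputed start date of medication is after the non-imputed end date of medication, then the start date will be set", the new value being the end date.
- **Start completely missing:** treated as concomitant, unless the end date is before IP (HD) or Day 1 (HP), in which case it is Prior.

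SAP Section 8.2.5 supplies the classes. Its definition of Prior is: "Those medications started and stopped prior to the initiation of the start of IP for HD and day 1 for HP will be denoted", followed by that label. For HD participants, a start at or after the first dose is enough for Concomitant. Records with incomplete dates default to Concomitant only when their status is unclear. Concomitant medications are tabulated by ATC level 1 and preferred term, by actual treatment group.

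**The concern.** The year-only start rule can place a start later than the medicine's own recorded end month. The reset exists to repair such records, but it is limited to end dates that were not imputed. An end recorded as month and year is always imputed, so it is never repaired. The result is an interval that starts on the first-dose day and ends before it, and the start alone then puts the medicine in the Concomitant class.

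The 8.2.5 default does not justify this outcome. An end month before the dosing month leaves no doubt that the medicine had stopped. At stake is the accuracy of the concomitant-medication summaries by treatment group, which SAP Section 6.1 keeps as the planned medication analysis.

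**Working it through.** No figure in the plan needs reproducing. The check applies the rules literally, with assumed dates.

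**Worked record (HD, first dose 20-Jun-2023; start 2023; end April 2023)**

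| Step | Rule | Result |
|---|---|---|
| 1 | Year-only start, same year as first dose | start = 20-Jun-2023 |
| 2 | Day-missing end | end = 30-Apr-2023 |
| 3 | Start after end, but the end is imputed | reset does not apply |
| 4 | 8.2.5: start at first dose | Concomitant |

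Three variants of this record isolate the cause:

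- End recorded as 20-Apr-2023: the reset applies, start = 20-Apr-2023, **Prior**.
- Start left completely blank, with the end before IP: **Prior** under the missing-start rule. Supplying the start year, which is extra information, turns the same medicine into Concomitant.
- Reset extended to imputed ends: start = 30-Apr-2023, end = 30-Apr-2023, **Prior**.

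**Comparison with the adverse-event rules in Appendix D.** A year-only AE onset in the dosing year is moved to the day after first dose only if the end date is after first dose or the event is ongoing. The AE reset applies to any stop date, imputed or not. The medication rules lack both protections.

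**How far it reaches.** All nine combinations of start precision (complete, month-year, year only) and end precision (the same three) were run. True start and end both lay before first dose, on a 3-day grid from 1 January 2022, and the day-missing start rule was read as comparing month and year. A start after the end arose in one combination only: year-only start with month-year end. For that combination:

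| Assumed first dose | Date pairs | Concomitant | Start after end | Remainder | Start-after-end pairs made Prior by extending the reset |
|---|---|---|---|---|---|
| 20 Jan 2023 | 8,256 | 753 | 0 | 753 − 0 = 753 | none to repair |
| 15 Jun 2023 | 15,753 | 2,150 | 1,275 | 2,150 − 1,275 = 875 | 1,275 of 1,275 |
| 15 Nov 2023 | 26,106 | 6,281 | 5,151 | 6,281 − 5,151 = 1,130 | 5,151 of 5,151 |

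The remainder consists of medicines whose recorded end month is the first-dose month. Their status really is unclear, and Concomitant is the stated default. The same counts (753, 875, 1,130) appear when the start is complete or month-year, so the defect separates cleanly from the default. The counts are shares of a uniform grid, not expected frequencies in the trial.

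**Such records can be collected.** With consent on Day −28, a first dose on 20-Jun-2023 puts consent on 23-May-2023. The 60-day look-back in SAP 8.2.5 then opens on 24-Mar-2023, and the 8-week look-back in Protocol 9.2.1 (56 days) opens on 28-Mar-2023 if Screening begins that day. A medicine used into April is in scope under either. Protocol 9.2.1 also collects "all medications used to treat HD regardless of timing".

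**The case against.** The strongest reply is that the gap is narrow and the intended result is visible. It needs a start with the month missing in the first-dose year, and an end missing only its day in an earlier month of that year. A complete end date, a year-only end or a first dose in January each exclude it. The definition of Prior and the missing-start rule both point to Prior as the intended class. All of this stands, and it limits the size. It does not remove the defect, because no stated rule produces the intended class for these records.

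A reader might infer four stronger claims, which the documents do not support:

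- **Old medicines are widely misclassified.** If "unless the month is the same as the date of the first dose then impute as the date of the first dose" were programmed without the year, a medicine taken from June 2019 to December 2020 would start on 20-Jun-2023, and about 1 in 12 old month-year records would match by chance. But the rule fills in a missing day, and that reading would overwrite a recorded year. The adverse-event rule shows the ordinary meaning: "If the year of AE onset = the year of initiation of the treatment and" only then is the month compared. Under that reading, month-year starts produced no start-after-end record. The documents also give no number of past medicines per participant.
- **False prohibited-medication deviations follow.** Protocol 9.2.2 records prohibited use as a deviation, and SAP 8.2.2 has the study team and sponsor classify deviations as the study proceeds. Nothing links either to imputed dates.
- **The HD versus HP comparison is distorted.** The partial-start rules name only the first dose, so an HP record would presumably keep its calendar start and be Prior. But 8.2.5 plans no HD–HP medication comparison.
- **The error is hidden.** Listings generally show the recorded partial dates, so the true end month remains visible there, although it would disagree with the table.

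The rule is also the same in both arms and acts on medicines stopped before dosing, so there is no reason to expect it to favour either arm.

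**Conclusion.** The rule is wrong as written, at minor severity. For HD participants with the date pattern described, Appendix D produces a start after the end and classes a medicine known to have stopped before dosing as Concomitant. This conflicts with its own missing-start rule and with its adverse-event rules.

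The number of affected records cannot be derived from the documents and is probably small. With the planned 20 participants per arm (Protocol 7.2), one affected participant can move a medication row by 1/20 = 5 percentage points. The effect is confined to the descriptive concomitant-medication summaries; the primary HD-CAB t-test does not use these dates.

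The conclusion rests on a literal reading of the reset rule and on imputed dates driving the classification, which is the purpose Appendix D states. It does not depend on the year-blind reading of the day-missing rule.

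**What to change.** In SAP Appendix D, medication section:

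1. Delete the word non-imputed from the reset rule. Alternatively, state first that a medicine whose end date, complete or imputed to its latest possible date, is before first dose (HD) or Day 1 (HP) is Prior, and that its start may not be imputed later than its end.
2. In the day-missing start rule, write month and year in place of month, so that it cannot be programmed without the year.

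The first change returns every start-after-end record in the check to Prior. Records that are truly unclear still default to Concomitant, because an end imputed within the first-dose month or year is never before the first dose.

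The cost is a few words and a small program change, with no new data and no protocol amendment. If the database is already locked, SAP Section 2 allows the change to be documented in the clinical study report.
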